## 6. Material and methods:

For this study, the Farmalarm App of the Inmoven group - Vall d'Hebrón Hospital will be used, adapted and updated by the main researchers of this study. The App will have the "rehabilitation" option where the user can consult the description of the exercise and view a demonstration video so that it can be carried out correctly at home, independently or with the help of a third person. The researchers will be responsible for The researcher of this study will also be registered as administrator of the App with permission to create users, contact them directly through chat or video-call and personalize the exercise program for each user. On the other hand, they will also have permission to consult the use data of the App by users. The App will also contemplate the option of confirming the completion of each proposed exercise and a small survey related to the effort used to complete it. The data obtained from these options will facilitate the customization of the exercise program.

The exercises that will be carried out with the App, in this study phase (Table 1), are described in previous works by the author [name] and colobradores (6). All possible exercises (description and demonstration video) will be included in the administration platform of the App and according to the capabilities of each user, the prescription of some exercises or others will be made, respecting their progression. In this

way, the aim is to personalize the therapeutic exercise program for each user, as well as modify the number of repetitions suggested and add facilitating or hindering suggestions to the same exercise.

Supino	Báscula pélvica antero-posterior Rotación de tronco superior Puente pélvica Puente con movimiento lateral Puente unilateral derecho Puente unilateral izquierdo Rotación del tronco inferior Flexión y extensión de rodillas Puente en pelota unilateral derecha Puente en pelota unilateral izquierda	  
Sedestación	Báscula pélvica antero-posterior Rotación de tronco superior Báscula pélvica medio-lateral Rotación tronco inferior Flexión lateral del tronco Alcance anterior Alcance lateral derecho Alcance diagonal derecho Alcance lateral izquierdo Alcance diagonal izquierdo	  

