Sedestación en pelota	Báscula pélvica antero-posterior Rotación de tronco superior Báscula pélvica medio-lateral Rotación tronco inferior Flexión lateral del tronco Alcance anterior Alcance lateral derecho Alcance diagonal derecho Alcance lateral izquierdo Alcance diagonal izquierdo	  

Table 1: Stability exercises of the lumbopelvic region

In this simple blind randomized controlled pilot study, participants will be recruited from users of the rehabilitation center where the study will be carried out (Neurorehabilitation Clinic - Sant Cugat del Vallés). To carry out this study, there is already an agreement signed between the Neurorehabilitation Clinic and the International University of Catalonia.

The following participation criteria have been defined for this pilot study Inclusion criteria:

- Medical diagnosis of stroke with cortical or subcortical, ischemic or hemorrhagic involvement with more than 6 months of evolution
- Clinical symptoms of hemiplegia or hemiparesis
- Over 18 years of age
- Ability to understand and execute simple instructions
- Score equal to or less than 10 in the Spanish version of the Trunk Impairment Scale 2.0
- Be a frequent user of smartphone or tablet. Failing this, the direct family member / caregiver is considered.

Exclusion criteria:

- Appearance of any disease or aggravation of any of the comorbidities that the patient presents that prevents rehabilitation (example: dialysis)
- Suffer a second episode of Stroke.
- Fractures in any of the lower extremities or important structural alterations in the trunk.
- Death

30 participants will be recruited. No sample calculation will be performed as it is a convenience sample for a pilot study and it is a value very close to the total number of users with Strokes of the center where the study will be carried out. Another limiting factor of the sample is that the users will be monitored daily or weekly by an investigator assuming a ratio of 30 users / 1 therapist. In the recruitment process, patients will be informed about the study, they will be asked to sign an informed consent and the randomization between the experimental group and the control group will be done by computerized lottery and with the following interventions:

Experimental Group: Use of App for the daily performance (Monday to Friday) of lumbopelvic stability exercises (Table 1) apart from the usual physiotherapy treatment for 3 months.

Control Group: Regular physical therapy treatment.

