For statistical analysis, all subjects will be included, regardless of subsequent events such as protocol violations, lost data, or loss to follow-up. Qualitative and quantitative descriptive statistics will be used to characterize the sample depending on categorical (eg.: sex) or numerical (eg.: age) variables. In the analysis of results, the missing data will be imputed applying the imputation criterion of the last observation made. The distribution of the sample will be calculated according to the Shapiro-Wilk test and parametric and / or non-parametric tests will be used to calculate the significance of the results. The significance level (p) will be 0.05, that is, a confidence level of 95% and 5% of acceptable error. For the purpose of this study, it is proposed to analyze the difference between means and standard deviations of the variables both at the initial time and at 6 and 12 weeks. Its statistical significance will be calculated by the Student's t test or the Mann-Whitney U test for paired data. For the analysis of the effectiveness of the interventions, the evolution obtained in the different groups will be compared with the same statistical tests for independent samples. To assess the correlation between variables, the calculation of Pearson's coefficient and / or Spearman's coefficient will be used.

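### The between-arm t test makes no provision for unequal variances; naming Welch's test would protect the stated 95% confidence if the arms turn out unequal (minor)

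*Combined protocol and SAP*

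**What the plan says.** All the relevant text is in section 6 (Material and methods) of the combined protocol and SAP.

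- **Tests.** For within-group change: "Its statistical significance will be calculated by the Student's t test or the Mann-Whitney U test for paired data". For effectiveness, "the evolution obtained in the different groups will be compared with the same statistical tests for independent samples". The between-arm parametric test is therefore Student's t for independent samples.
- **Check before testing.** "The distribution of the sample will be calculated according to the Shapiro-Wilk test". This concerns shape. Nothing is said about equality of variances, and Welch's test is not mentioned.
- **Level.** "The significance level (p) will be 0.05, that is, a confidence level of 95% and 5% of acceptable error". Sidedness is not stated, and no interval for the between-arm difference is explicitly planned.
- **Size and allocation.** "30 participants will be recruited", and "No sample calculation will be performed as it is a convenience sample for a pilot study". Allocation is described only so far: "the randomization between the experimental group and the control group will be done by computerized lottery". No ratio, blocking or arm sizes are given.
- **The App arm.** Only this arm adds the App exercises to usual physiotherapy. For those exercises "the aim is to personalize the therapeutic exercise program for each user", and use is graded as low, regular or good over 0 to 60 days.

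**The concern.** Student's t for independent samples normally pools the two sample variances. Pooling is harmless when the arms are equal in size or the true variances are equal. When neither holds, the standard error is wrong. It is too small if the more variable arm is the smaller, and too large if that arm is the larger.

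Both conditions are possible here. A benefit that varies with adherence and with the personalised programme would widen the spread of change scores in the App arm, and the text does not guarantee equal arms. What is at stake is the precision attached to the estimated App effect. An interval labelled 95% could cover somewhat less or somewhat more, depending on how the lottery falls. The Shapiro-Wilk check would not reveal this.

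**Working it through.** The plan has no power or sample-size figure to reproduce. Its only related figure is the 0.05 level (95% confidence), taken here as two-sided.

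**Inputs.** From the plan: N = 30, level 0.05, Student's t on change. Assumed: simple 1:1 allocation, normally distributed change scores, and r = App SD / control SD. The plan gives no SD.

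**1. What SD ratio is plausible?** Let the control SD be 1 and D the benefit at full adherence in control SDs, with benefit independent of the other variation.

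- Adherence spread evenly over 0–100%, benefit proportional to it: r = √(1 + D²/12). D = 1, 2, 3 gives 1.04, 1.15, 1.32.
- Half respond fully and half not at all: r = √(1 + D²/4). D = 1, 2 gives 1.12, 1.41.

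A range of about 1.0 to 1.5 is reasonable.

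**2. How likely are unequal arms?** With Binomial(30, 0.5):

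- exactly 15/15: 1 − 0.8555 = 14%
- 12/18 or worse, either way: 2 × 0.1808 = 36%; with the App arm the smaller: 18%
- 10/20 or worse, either way: 9.9%; with the App arm the smaller: 4.9%

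**3. Why direction depends on the split.** On average Student's t uses the variance [(n₁−1)r² + (n₂−1)]/(n₁+n₂−2) × (1/n₁ + 1/n₂) for the difference in means. The true variance is r²/n₁ + 1/n₂, where arm 1 is the App arm. At r = 1.5 (r² = 2.25):

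- App 12, control 18: used (11×2.25 + 17)/28 × (1/12 + 1/18) = 1.491 × 0.1389 = 0.207; true 2.25/12 + 1/18 = 0.243. SE ratio √(0.207/0.243) = 0.92, so too small.
- App 18, control 12: used (17×2.25 + 11)/28 × 0.1389 = 1.759 × 0.1389 = 0.244; true 2.25/18 + 1/12 = 0.208. SE ratio 1.08, so too large.
- 15/15: used 1.625 × 2/15 = 0.217; true 3.25/15 = 0.217. No error.

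**4. Coverage.** By simulation, 200,000 normal trials per setting. A shift in mean does not alter either variance, so coverage is 100% minus the rate at which the test rejects the true difference.

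| App/control | Student, r = 1 | r = 1.25 | r = 1.5 | Welch, r = 1 to 1.5 |
|---|---|---|---|---|
| 15/15 | 95.0% | 94.8% | 94.9% | 94.9–95.1% |
| 12/18 | 95.0% | 93.9% | 93.0% | 95.0% |
| 18/12 | 95.1% | 95.9% | 96.4% | 95.0–95.1% |
| 10/20 | 95.0% | 93.1% | 91.4% | 94.8–95.0% |
| 20/10 | 95.0% | 96.5% | 97.2% | 95.0–95.1% |

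Averaged over all splits of a simple lottery, Student's error rate is 5.1% at r = 1.25 and 5.4% at r = 1.5. The effect therefore lies in the split that happens, not in the design on average.

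**5. Cost of Welch when variances are equal.** For true differences of 0.5 to 1.0 SD, power falls by at most 0.2 points at 15/15, 0.3–0.9 at 12/18 and 0.7–1.9 at 10/20 (at 1 SD: 70.2% against 68.3%).

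**6. Power when variances differ.** With r = 1.5 and a difference of one control SD, Student against Welch is 50% against 56% at 18/12, and 56% against 48% at 12/18. Student's apparent gain at 12/18 comes from its too-small standard error.

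**The case against.** The strongest objection is that the mechanism does not produce false positives. Variable adherence and personalisation widen the App arm's spread only if the App changes outcomes. If it does nothing for anyone, the arms are exchangeable, variances are equal, and Student's t holds 5% at every split. A reader might compute type I error of 7% or 8.5% (12/18, r = 1.5 or 2) and conclude that the trial's 5% level fails. That requires a mean effect of zero together with an inflated SD, so that the App harms some patients as much as it helps others. The documents suggest no such thing. This objection stands, and it leaves the point about coverage when the App has some effect.

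Other objections also stand in part:

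- **Spread.** The documents do not say that the App arm will vary more. Section 7 describes usual rehabilitation as fitted to each person's condition and needs, so control care is individualised too. A ratio of 2 would need implausible benefits: under even adherence D = √(12×3) = 6 control SDs.
- **Arm sizes.** A reader might take the lottery to mean that arm sizes are left to chance. The text does not say so. Drawing 15 of 30, or blocking, would make the issue negligible for the main outcomes. It would not do so for the accelerometer gait measures, which are taken only in patients who reach the required score.
- **Pooling.** That Student's t means the pooled form is the usual reading, not a statement in the plan.
- **The other branch.** Welch does not repair the Mann-Whitney comparison, which has a similar sensitivity (at r = 1.5, 6.1% rejection at 12/18 and 4.2% at 18/12, equal locations). Several outcomes are ordinal or counts, so that branch may be used often.

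**Conclusion.** A minor point, but sound. As written, the plan leaves the between-arm t test without protection against unequal variances, and its allocation text does not rule out unequal arms. With SD ratios of about 1.0 to 1.5 and a simple 1:1 lottery, nominal 95% confidence becomes about 93–95% with the smaller App arm at 12/18 and 95–96% with the larger App arm at 18/12. Welch gives about 95% in both. At 15/15 the difference is negligible.

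The conclusion rests on the assumed SD ratio, the assumed allocation scheme and the usual pooled reading of Student's t. It does not show that the trial's 5% error rate is broken, and it does not establish that App-arm variance will be larger. It shows only that a nearly costless choice of test removes the dependence on both.

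**What to change.** In the statistical paragraph of section 6, state that the independent-samples t test is Welch's unequal-variance test, reported with the difference in mean change and its 95% CI, and applied without a preliminary test of variances. Stating the allocation ratio and any blocking would also let readers judge whether unequal arms are possible.

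The cost is a short text edit and a software option, with no new data and no change in trial conduct. Statistically, the price is at most about 2 points of power, if variances are in fact equal and the arms are as uneven as 10/20. The edit leaves the Mann-Whitney branch as it is, so results from that branch still need cautious reading where spreads differ.

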## 7. Analysis of results:

According to the existing literature, performing muscle exercises for lumbopelvic stabilization leads to improvements in the balance in sitting, standing and gait in individuals with stroke. These results can be translated into the increase in participation in the ADL and the increase in the CV, factors to be taken into account in these individuals since their sequelae are usually highly limiting and chronic.

Usually, individuals who have suffered a stroke receive rehabilitation, by different disciplines where we find physiotherapy, according to their conditions and needs and with the common objective of achieving the maximum level of autonomy. Knowing that stroke patients can present chronic sequelae, their rehabilitation is perpetuated over time. It is thought that the use of an App can provide continuity to rehabilitation in its chronic phase, monitor and accompany the clinical evolution of the patient by the therapist. On the other hand, one can think that perhaps it is a method that allows reducing the resources, expenses in transfers and occupation of the rehabilitation center by chronic users.

The App will provide specific guidelines for carrying out lumbo-pelvic stabilization exercises and the possibility of viewing demonstration videos, with this it is intended to facilitate and encourage the performance of muscle exercises by the patient independently or with the help of a family member or caregiver. On the other hand, the patient will find a means that allows him to be in direct contact with the therapist in case of doubts about his rehabilitation process, as well as the therapist can contact the patient to monitor and follow up. In case of observing high levels of adherence to the use of the App as well as better results compared to conventional therapy, the use of the App as a new tool in neurorehabilitation can be considered. Even if chronicity leads us to think about maintaining physical condition, it is planned to find better results among individuals who will use the App as a therapeutic accompaniment for autonomous performance of muscle exercises for lumbopelvic stabilization adjacent to regular physical therapy.

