#### 5. Hypothesis:

The hypothesis of the present study project is: to. The use of an App, adapted to the abilities and needs of individuals with stroke, improves adherence to its use for carrying out specific therapeutic exercises. b. Muscular stability exercises of the lumbopelvic area performed at home monitored by means of an App improve the

perception of the QoL of individuals who have suffered a stroke in the chronic phase of their evolution compared to the usual follow-up of this type of individuals. c. Muscular stability exercises of the lumbopelvic area performed at home monitored by an App increase the functionality and participation in the ADL of individuals who have suffered a stroke in the chronic phase of their evolution compared to the usual follow-up of this type of individuals. d. Muscular stability exercises of the lumbopelvic area performed at home monitored by an App improve the balance in sitting and standing and reduce the number of falls of individuals who have suffered a stroke in the chronic phase of their evolution compared to the usual monitoring of this type of individuals. and. Muscular stability exercises of the lumbopelvic area performed at home monitored by means of an App improve the gait of individuals who have suffered a stroke in the chronic phase of their evolution compared to the usual follow-up of this type of individuals.

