The information on the usual physiotherapy treatment will be collected together with the variables to be studied. At the end of the study, the description of the usual treatment, neuromotor development treatment, will be disclosed, which usually includes techniques for modulating the muscle tone of the affected body, postural control exercises, facilitation of functional movement and practice of tasks including walking.

To guarantee the blinding characteristic, the evaluations will be carried out by a third non-investigating person. The following variables will be studied through selected tests and questionnaires:

- Adherence to the use of the App by individuals from the EG: Data extracted by the administration panel of the App and System Usability Scale. Optimal use (100%) is considered 5 days / week, that is, a use from 0 to 20 days in 12 weeks months will be considered low adherence (0-33%), from 21 to 40 days (33-66%) regular adherence and 41 to 60 days (66-100% :) good adherence.
- QoL: EuroQol 5 dimensions 5 levels.
- Participation in AVD: Barthel Index.

- Functionality: Rankin scale.
- Sitting balance: Spanish versions of the Trunk Impairment Scale 2.0 and Function in Sitting Test.
- Standing balance: Spanish version of the Postural Assessment Scale for Stroke Patients, Berg Scale
- Record of the number of falls.
- Gait: stepping section of the Brunel Balance Assessment test and if they reach a score of 6 they will be evaluated with the G-Walk accelerometer (duration of double and individual support, cadence of the step, gait speed, stride length, length of step and elaborate steps).

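### The plan records no adverse events or injuries beyond a bare falls count, and lets the App be considered on adherence and undefined better results with no harm condition

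*Combined protocol and SAP*

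**What the plan says.** Section 7 (Analysis of results) gives the only statement of what would carry the App forward. The condition is "In case of observing high levels of adherence to the use of the App as well as better results compared to conventional therapy", and the consequence is that "the use of the App as a new tool in neurorehabilitation can be considered". Section 6 (Material and methods) bands adherence as low, regular or good. Nothing says what counts as better results or on which scale.

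The variable list in section 6 covers adherence, quality of life, daily activities, functionality, sitting and standing balance, gait and falls. The entry for falls reads, in full, "Record of the number of falls". Its role is set by hypothesis d in section 5, that the exercises "improve the balance in sitting and standing and reduce the number of falls of individuals". The statistical paragraph of section 6 compares change between groups by t test or Mann-Whitney U and has no separate analysis of harms.

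Participants must have hemiplegia or hemiparesis and meet this criterion: "Score equal to or less than 10 in the Spanish version of the Trunk Impairment Scale 2.0". The App describes and demonstrates each exercise "so that it can be carried out correctly at home, independently or with the help of a third person", Monday to Friday for 3 months. The Table 1 menu includes reaching while seated on a ball.

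Serious events do appear in section 6, but only under the exclusion criteria: "Appearance of any disease or aggravation of any of the comorbidities that the patient presents that prevents rehabilitation", "Suffer a second episode of Stroke", lower-limb fracture, and death.

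**The concern.** People selected for poor trunk control may do balance-challenging exercises at home without a therapist present. Section 3 itself links balance deficit and fall risk to poor quality of life in chronic stroke. A pilot of such a programme should be able to say what happened to the people who did it. Followed exactly, this plan yields a number of falls per person and nothing on pain, strain, injury or unplanned care. It also cannot say whether any fall occurred during an exercise. These details are hard to recover once the trial is over.

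Section 7 then allows the App to be considered on adherence and better results. With many scales and no definition, gains on one or more of them could be read as sufficient while falls were no better or were worse, and while other harms had not been looked for.

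**Working it through.** **Figures stated in the plan.** The sample size of 30 comes with no power, effect size or standard deviation, so there is nothing to reproduce. The adherence scale reproduces: 5 days × 12 weeks = 60 days; 20/60 = 33.3% and 40/60 = 66.7%, matching the bands apart from rounding.

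**Assumptions.** The allocation ratio is not stated; 1:1 gives 15 per arm. The test level is 0.05, taken as two-sided. All event rates below are assumed, because the documents give none.

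**Exposure.** 15 users × 60 days = 900 planned home exercise days, at full adherence.

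**Can the falls comparison reveal excess falls?**

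- *Fall counts.* Simulated negative-binomial counts (dispersion 1, 3,000 runs, Mann-Whitney U), counting a detection when p ≤ 0.05 and the App mean is higher. For a doubled rate, power is 0.14, 0.18 and 0.22 at control means of 0.3, 0.5 and 1.0 falls per person. For a rate 1.5 times as high, it is 0.06, 0.08 and 0.09.
- *Proportion of fallers.* Normal approximation: power = Φ{[(p₂ − p₁) − 1.96·√(2p̄(1−p̄)/n)] / √[(p₁(1−p₁) + p₂(1−p₂))/n]}. For 20% versus 40% and n = 15: 1.96 × √(2 × 0.3 × 0.7/15) = 0.328; √((0.16 + 0.24)/15) = 0.163; (0.200 − 0.328)/0.163 = −0.78; Φ = 0.22. Exact Fisher power is 0.11. For 30% versus 50%: 0.19 and 0.10. For 30% versus 60%: 0.37 and 0.23.

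A non-significant falls result would therefore not be evidence of safety.

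**What could event-level recording deliver?** If no App user had a related event, the one-sided 95% upper bound on the per-person risk is 1 − 0.05^(1/15) = 0.181, about 18% (two-sided: 1 − 0.025^(1/15) = 0.218). The chance of seeing at least one event in 15 people is 1 − (1 − p)^15: 14%, 26%, 54% and 79% for true risks of 1%, 2%, 5% and 10%. Recording would not make the pilot a safety trial, but it would let the report state what was seen and how little that excludes.

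**Exclusion criteria against the analysis set.** Several exclusion criteria are worded as events that arise later (a disease appearing, a further stroke, death). If they are applied after enrolment, the participants with the worst events leave. The statistical paragraph of section 6, however, keeps every subject whatever happens afterwards and fills gaps with the last observation, which would then be a score from before the event. The two passages conflict on that reading and must be reconciled.

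**The case against.** The best reply is that harm is not absent from the criterion. Fewer falls is a stated hypothesis, falls are compared between groups, and they therefore belong among the results that must be better. This stands, and a reader who infers that harm plays no part in section 7 goes too far. What remains is that better results is undefined, so falls need not decide the matter.

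A reader might also infer that the defect is pooling exercise falls with other falls. The documents do not support that. In a randomised comparison the all-cause count measures the net effect, and falls caused by the App appear as an excess in its arm. Take assumed counts of 15 control falls against 6 daily-life plus 9 exercise falls: 15 versus 15 correctly answers hypothesis d with no net reduction. Comparing 6 with 15 would set part of one arm against all of the other. Attribution is useful beside the total, not in place of it.

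Three further inferences fail.

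- *The plan would endorse a harmful programme.* The text says only that use may be considered, after a pilot.
- *Controls go unmonitored, so harms would surface in one arm only.* Chat and video-call are App features, but section 6 describes monitoring at 30 users per therapist, and 30 is the whole sample. Whether controls are included is left open.
- *Every App user does ball exercises.* Section 6 prescribes from the menu according to ability and progression.

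Consent pages were not available, so any safety text there could not be checked.

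**Conclusion.** The point holds in this form: in the available text, no adverse event or injury is collected beyond an uncharacterised falls count, no harm analysis is planned, and section 7 sets no harm condition while leaving better results undefined. The all-cause falls comparison is right in kind, but at an assumed 15 per arm it would detect a doubled fall rate only about 14% to 22% of the time under the rates tried. It cannot show injury, pain or the circumstances of a fall at any sample size. The power figures rest on assumed rates and dispersion; the gap in data collection does not. The change should be made before recruitment, because information not collected in either arm cannot reliably be reconstructed. The exclusion criteria and the inclusion of all subjects also need to be reconciled.

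**What to change.** 1. **Section 6, variables.** Keep the all-cause falls count as the between-arm comparison and state how and over what period falls are recorded. Add a short form, completed by the participant or caregiver in both arms at the 6- and 12-week visits. It lists each fall (date, activity at the time, injury or medical contact) and any pain, injury or unplanned care. It is returned sealed to the investigator. The blinded evaluator should not collect it: a fall during an App exercise reveals allocation, and someone unblinded at week 6 would go on to score the week-12 tests.
2. **Section 6, analysis.** Report these events, and the serious events now named only as exclusion criteria, by arm in one descriptive table. Show exercise-related events in the App arm as a supplement to the total, and state the precision (0 of 15 still allows about 18%). List separately any event known only through App contact. State whether the exclusion criteria apply after enrolment, and reconcile them with the inclusion of all subjects.
3. **Section 7.** Add that considering the App also takes into account the falls and adverse events reported by arm.

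The cost is a few minutes at visits already planned, one extra table and a sentence. The limitation is that events are self-reported and depend on recall. No rule for managing individual participants is proposed.
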